
Intercostal nerve cryoablation is considered a relatively new treatment for postoperative pain in patients undergoing minimally invasive mitral valve surgery. One of the first studies of cryoneurolysis was conducted back in 1974 in thoracic surgery [9]. In 76 patients, the use of intercostal cryoablation resulted in a significant reduction in postoperative opioid analgesic consumption. These results were subsequently confirmed in several other studies and the data were retrospective. In 2000, a prospective randomized controlled trial was published involving 30 patients who underwent minimally invasive mitral valve surgery or minimally invasive coronary artery bypass grafting and underwent intercostal

cryoablation. According to the results, a decrease in postoperative pain syndrome was observed, and less painkillers were required [10].

In the study O'Connor LA et al. in patients undergoing surgical stabilization of the ribs, cryoablation of the intercostal nerves resulted in a 25% reduction in opioid analgesics consumption compared with patients who received an extrapleural catheter, and pain scores were reduced by 22% in the cryoablation group [7]. Similar results (cryoablation made it possible to significantly reduce morphine consumption compared to the control group and reduce pain) were also described in recent retrospective studies through 2023 in other patient groups: patients who have undergone pulmonary resection using single-port thoracic video-assisted access, where cryoablation was used as a method of postoperative pain relief [8] and patients undergoing lung transplantation [12].

In the FROST study for 2021 the use of this method in patients with lateral thoracotomy showed significant improvement in spirometry parameters (FEV1, FVC) after 48 hours, as well as 30 and 60 days after surgery [6]. Studying the influence of pain was not the main objective of this work; pain was assessed using VAS and did not show a difference. However, improvement in breathing parameters in the early postoperative period may indirectly be associated with a lower level of pain and a more comfortable state of the patient; the consumption of opioid analgesics was not properly assessed in this study.

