In 2021 Peter I Cha and others published a systematic review of 23 studies on the effectiveness of intercostal cryoneurolysis in patients with pectus excavatum, lateral thoracotomy, post-thoracotomy pain syndrome, traumatic rib fracture and chest wall malignancy. Most studies have demonstrated a reduction in opioid analgesic use with intercostal nerve cryoablation compared with traditional pain management techniques. In patients requiring lateral thoracotomy, intercostal cryoablation results in decreased opioid analgesic dosage (grade 2A) and improved pain scores (grade 2C) postoperatively (PICO guidelines) [11].

Finding an effective and at the same time simple strategy for pain relief in the early postoperative period in patients undergoing minimally invasive mitral valve surgery is an urgent task; it is advisable to conduct a prospective clinical study with a well-thought-out design in this direction.

Study design

A single-center pilot prospective randomized clinical trial is planned, with a 1:1 allocation ratio.

Objectives

To determine whether cryoablation of intercostal nerves provides a clinically significant analgesic effect, which is reflected in a decrease in opioid analgesics consumption and in a decrease in pain according to VAS in patients undergoing minimally invasive mitral valve surgery. To obtain preliminary data for planning a subsequent larger prospective randomized trial.

Research aims:

1. Conduct a comparative analysis of the data on the opioid analgesic consumption necessary for pain relief when using cryoablation of intercostal nerves and the standard treatment protocol in patients with minimally invasive mitral valve surgery.
2. To conduct a comparative assessment of pain syndrome according to VAS in patients in the intercostal nerve cryoablation groups and the standard treatment protocol in patients with minimally invasive mitral valve surgery.
3. Assess spirometry parameters (FEV1, FVC) before surgery, 48 hours after surgery and before discharge when using cryoablation of intercostal nerves and the standard treatment protocol in patients with minimally invasive mitral valve surgery.
4. To evaluate the incidence of side effects and the need for inotropic and vasopressor support in the early postoperative period in the intercostal nerve cryoablation and standard treatment protocol groups in patients undergoing minimally invasive mitral valve surgery.

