5. To evaluate the duration of mechanical ventilation in the postoperative period when using cryoablation of intercostal nerves and the standard treatment protocol in patients with minimally invasive mitral valve surgery.
6. Assess the length of stay in the ICU and the duration of hospitalization when using cryoablation of intercostal nerves and the standard treatment protocol.
7. Assess the presence of chronic post-thoracotomy pain syndrome in the postoperative period after 2 and 6 months and the presence of side effects after cryoablation of intercostal nerves (paresthesia in the area of surgical access and in the right arm).

Research participants

30 patients (15 patients in each group) who are scheduled to undergo minimally invasive mitral valve surgery under cardiopulmonary bypass.

Inclusion criteria

- Written informed consent;

- Minimally invasive mitral valve surgery.

Non-inclusion criteria:

- patient refusal;
- pregnancy;
- treatment with antidepressants or epileptic drugs;
- depression, which can significantly affect the perception of pain;
- chronic use of analgesics;
- participation in competing randomized clinical trials.

Exclusion criteria:

- Extended mechanical ventilation, more than 12 hours.

Randomization, allocation, blinding

A block will be used to distribute participants into groups randomization with block lengths of 2 and 4. Masking will be performed for the statistician. Sample size calculation was not performed because no data were available to estimate sample size.

Description and rationale for the route of administration, dosage, dosage regimen and course of treatment

Patients undergoing minimally invasive mitral valve surgery while on cardiopulmonary bypass will be randomized into two groups:

1. Patients receiving cryoablation of intercostal nerves (CryoINB) as a method of pain relief.
2. Patients who will undergo a standard pain management protocol.

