- Dynamics of spirography (FEV1, FVC) before surgery, 48 hours after surgery, before the patient's discharge
- Frequency of side effects (nausea, vomiting, etc.)
- Need for inotropic/vasopressor support
- Duration of mechanical ventilation
- Duration of ICU stay
- Duration of hospital stay
- Follow-up after 2 and 6 months (CPPS, numbness in the right arm and in the area of surgical access)

Statistical analysis

Comparisons of continuous outcomes will be made using the Mann-Whitney test for non-normal variables and the Welsh t test for normal variables. Comparisons of binary outcomes will be made by the chi-square test or Fisher's exact test.

Data processing

All information will be collected by staff using paper documentation, the data of which will then be entered into an electronic database.

Initial data

1. Demographic indicators: age, gender, height, weight, body mass index.
2. Disease severity: left ventricular ejection fraction, left ventricular EDV, presence of mitral regurgitation, degree of mitral regurgitation, peak mitral valve gradient, pulmonary artery pressure, FAC (Fractional Area Change), history of cardiac surgery, NYHA class, EuroSCORE II risk.
3. Concomitant diseases: myocardial infarction, arterial hypertension, diabetes mellitus, atrial fibrillation, ventricular extrasystole, COPD, chronic kidney disease, stroke, epilepsy.
4. Taking the following medications: antidepressants, antiepileptic drugs, long-term use of NSAIDs (more than 14 days), opioid analgesics.

During the operation:

1. Type of surgery (mitral valve repair or replacement).
2. Time of heart-lung bypass (minutes).
3. Aortic occlusion time (minutes).
4. Minimum temperature during surgery.
5. Dose of fentanyl per operation (mg/kg).
6. Inotropic index.

Period of hospitalization and stay in the ICU:

1. Dose of opioid analgesics 48 hours after surgery (morphine in MME).
2. Assessment of pain intensity using a visual analogue scale (VAS) after extubation, 6, 12, 24, 36, 48 hours after surgery.
3. Duration of mechanical ventilation (in days).
4. The presence of side effects (nausea, vomiting).
5. Need for inotropic and vasopressor support, VIS.
6. Surgery complications (pulmonary edema, bleeding, febrile seizures, heart failure, respiratory failure, myocardial infarction).
7. Duration of stay in the ICU (in days).
8. Duration of hospitalization (in days).
9. The result of spirometry before surgery, 48 hours after surgery and before

discharge.

Ethical issues

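### The unadjusted test stated for every continuous outcome does not use the collected preoperative FEV1 and FVC as a covariate; for roughly normal data this usually gives up some precision on a secondary endpoint

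*Protocol*

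**What the plan says.** The Statistical analysis section gives one rule for all continuous outcomes: "Comparisons of continuous outcomes will be made using the Mann-Whitney test for non-normal variables and the Welsh t test for normal variables". It mentions no covariate, ANCOVA or repeated-measures model.

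FEV1 and FVC are continuous and fall under this rule. They appear in three places:
- Research aims, item 3: "Assess spirometry parameters (FEV1, FVC) before surgery, 48 hours after surgery and before discharge".
- Secondary endpoints: "Dynamics of spirography (FEV1, FVC) before surgery, 48 hours after surgery", and again before discharge.
- Period of hospitalization and stay in the ICU, item 9: "The result of spirometry before surgery, 48 hours after surgery", and again before discharge.

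The preoperative value is therefore planned data. The Protocol does not say whether *dynamics* means the change from that value or the postoperative value itself.

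Research participants sets the size at "30 patients (15 patients in each group", and Study design describes a trial "with a 1:1 allocation ratio". No sample size calculation was made. The Objectives define the analgesic effect by "a decrease in opioid analgesics consumption and in a decrease in pain according to VAS", so spirometry is not part of that definition. The Background does report that an earlier randomized trial of the method "showed significant improvement in spirometry parameters (FEV1, FVC) after 48 hours".

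**The concern.** A two-sample test on a repeated measurement gives the preoperative value a fixed weight: 1 if the change is tested, 0 if the postoperative value is tested. ANCOVA estimates the weight from the data. Under randomization all three estimate the same treatment difference without bias, so the question is only how precisely.

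With 15 per arm the interval for a spirometry difference will be wide. Spirometry is a named research aim, the method's earlier trial showed an effect on it, and this pilot is meant to inform a larger trial. A narrower interval would be useful, and the measurement needed for it is already planned.

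**Working it through.** The Protocol states no SE, power or sample size for this endpoint, so there is no figure to reproduce.

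**Inputs.** From the Protocol: N = 30, 1:1 allocation, preoperative value collected. Assumed, because the Protocol gives neither: pre/post correlation r = 0.5, 0.7, 0.8, and post/pre SD ratio k = 0.7 to 1.4. Postoperative SD is set to 1. The formulas assume normality and equal variance in the arms.

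**Formulas (SE relative to a test on the postoperative value).**
- Change: sqrt(1 + 1/k² - 2r/k)
- ANCOVA: sqrt((1 - r²)(N - 3)/(N - 4)), with 27/26 = 1.0385 at N = 30

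**ANCOVA against the postoperative value.** sqrt(0.75 × 1.0385) = 0.883, sqrt(0.51 × 1.0385) = 0.728, sqrt(0.36 × 1.0385) = 0.611. The SE falls 12, 27 and 39%.

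**ANCOVA against change.** At k = 1 the change SE is sqrt(2 - 2r) = 1.000, 0.775, 0.632. Dividing gives the first row; the others follow in the same way.

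| k (post/pre SD) | r = 0.5 | r = 0.7 | r = 0.8 |
|---|---|---|---|
| 1.0 | 0.883 | 0.940 | 0.967 |
| 0.85 | 0.803 | 0.848 | 0.863 |
| 0.7 | 0.695 | 0.713 | 0.704 |
| 1.2 | 0.951 | 1.002 | 1.017 |
| 1.4 | 0.989 | 1.019 | 1.009 |

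**Worst case.** No fixed weight gives a residual variance below 1 - r², so ANCOVA can lose only the estimation factor. That is sqrt(27/26) = 1.019, or 2.1% in CI width with the lost degree of freedom. If only 24 patients are analysed it is sqrt(21/20) = 1.025, or 2.8% in CI width. ANCOVA is worse than the postoperative value only for r below about 0.19. It is worse than change for r above about 0.93 (k = 1), between 0.69 and 0.91 (k = 1.2), or between 0.55 and 0.83 (k = 1.4).

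**Interval half-width in postoperative SDs** (simulation, 15 per arm, r = 0.5 / 0.7 / 0.8):
- Welch on change: 0.74 / 0.58 / 0.47 at k = 1; 0.69 / 0.54 / 0.45 at k = 1.2
- ANCOVA: 0.66 / 0.54 / 0.45
- Welch on the postoperative value: 0.74 throughout

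**Unequal variances.** With assumed arms of 10 (more variable) and 14, r = 0.7 and residual SD ratio 1.5 or 2, ordinary ANCOVA has type I error of about 6.8% or 7.9%. Welch stays near 5% and ANCOVA with an HC3 robust SE near 4.5%. With 15 and 15 and ratio 2, ordinary ANCOVA is at 5.3%.

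**What HC3 costs.** I simulated 40,000 bivariate normal trials per setting, 15 per arm and equal variances. ANCOVA with HC3 had type I error of about 4% and mean half-widths of 0.69 / 0.57 / 0.48, about 5% wider than ordinary ANCOVA. Against Welch on change that is about -7 / -1 / +2% at k = 1 and 0 / +6 / +7% at k = 1.2.

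**Skewed data** (assumed lognormal, skewness about 1.7, effect 0.75 SD). Power for Mann-Whitney on the postoperative value / Mann-Whitney on change / linear ANCOVA is 65/44/57% at log-scale r = 0.3, 65/57/64% at 0.5, 65/78/78% at 0.7 and 65/90/88% at 0.8. There is no consistent gain.

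**The case against.** The strongest reply is that nothing is wrong: a valid standard test is used for a secondary endpoint of a 30-patient pilot, and preferring ANCOVA is close to taste. That stands as a limit on severity. It does not remove the point, because the Protocol itself names the method and collects the value that the method leaves out.

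Four further objections hold and shape the conclusion.
- *Dynamics* reads most naturally as change. A reader might take the 27 to 39% reductions as the expected gain, but those require the postoperative value alone to be tested, which the Protocol nowhere says.
- A reader might infer that ANCOVA is always better. If postoperative SDs exceed preoperative ones, four of the six cells above show no gain.
- Replacing both branches by ordinary ANCOVA would lose up to 8 points of power in the skewed example (65 against 57%). It would also drop Welch's protection against unequal variances. This matters because the exclusion criterion of ventilation beyond 12 hours can arise only after surgery, so the analysed arms may be smaller and unequal.
- A reader might infer that any later adjustment would be post hoc. A statistical analysis plan not shown here could name it before the data are seen, so the document does not support that.

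Nor does the document support a reading of bias, or of lost planning data: SDs and the correlation can be obtained whichever test is used.

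**Conclusion.** The point holds as a modest loss of precision, not an error of validity. It is limited to FEV1 and FVC and to roughly normal data. The -12 to -3% lead figure assumes that change is tested and the SDs are equal. Whether the SE gain is larger or vanishes depends on the SD ratio and correlation, neither of which the Protocol gives.

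Those percentages describe ordinary ANCOVA. With a robust SE, the reported interval keeps a clear advantage over change mainly when r is moderate or the postoperative SD is the smaller one. Against the postoperative value alone it stays narrower at every r examined. The change is worth considering; the trial's main conclusion does not depend on it.

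**What to change.** Add a sentence to the Statistical analysis section. Where FEV1 and FVC are roughly normal, the 48 h and pre-discharge values will be compared on the absolute scale by linear ANCOVA with treatment and the preoperative value. The model will use a small-sample heteroscedasticity-robust SE (for example HC3), and the adjusted difference will be reported with its 95% CI. Keep Mann-Whitney for clearly skewed data and the Welch test as a sensitivity analysis.

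Linear ANCOVA gives the same treatment effect for the value and for the absolute change, so it also settles what *dynamics* means for this comparison. This does not extend to percent change or ranks, so the scale should be fixed before the data are seen.

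Cost: no new measurement and one degree of freedom. Under normality and equal residual variance, the expected SE is at most 1.9% larger at N = 30 and 2.5% larger at N = 24. HC3 adds about 5% to the interval width at 15 per arm, as the price of robustness.
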